10.3 Interim Analysis

Patients will be continuously monitored for safety and toxicity as we enroll up to 6 patients for the study. A stopping point will be enforced if 2 or more subjects develop infections requiring IV antibiotics or require hospitalization.

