3.4 Primary Safety Endpoints

The primary safety endpoint for the study will be the rate of infection or hospital admission within 30 days that are felt to be directly related to the procedure.

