7.1 Follow-up Procedures

Patients will be followed for safety assessments at post-operative day 1, and at visits 3, 4, and 5. Data collection will include routine treatment data, assessment of urinary obstruction requiring Foley catheter placement as well as signs or symptoms of infection requiring additional antibiotics or hospital admission felt to be directly related to the procedure.

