10.2 Statistical Methods

Statistical analysis: The correlation of biopsy tissue histopathology with intraprostatic MRI findings will be estimated using binomial evaluation for True Positive, False Positive, True Negative, False Negative values to report Sensitivity, Specificity, and Positive as well as Negative Predictive value for parametric MRI findings relative to correlated histopathology. These data will be used for reporting the study results in regards to Specific aim 1, The infection rate and hospitalization rate within 30 days due to the procedure will be collected for expected acute events (AE's) and these data will be used for reporting the study results for specific aim 2 evaluation the transperineal use of Uronav to determine if the transperineal biopsy approach results in a reduced rate of infection or hospitalization compared to standard transrectal biopsies.

Any deviations from the previously described statistical plan will be described and justified in a protocol amendment.

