11.0 Risk Analysis

Clinical information from subjects will be recorded onto Case Report Forms and subsequently transferred into OnCore. Patients who additionally consent to a separate Urology Registry will have their data added to the Urologic Oncology & Minimally Invasive Therapies Database for UHHS Faculty.

Should any unanticipated adverse events occur during the course of the study, the clinical research coordinator will ensure that they are documented by the investigator and reported to the appropriate IRB per its then-current guidelines. If the determination is made that an unanticipated adverse event presents an unreasonable risk to subjects, the clinical evaluation will be paused, or if deemed appropriate (to enable further investigation), the subject will be withdrawn as soon as safely possible.

Adverse events, grade 2 and above, will be captured in OnCore and will be reported in accordance with the Data and Safety Monitoring Plan (DSMP) that is approved by the Cancer Center Protocol

Review and Monitoring Committee (and aligned with the NCI-approved plan). All monitoring and reporting will be compliant with policies presented in the most current version of the CCCC Clinical Trials Operations Manual, so that an independent assessment can be made of study activities. The study will be updated to remain compliant with any changing rules/policies of the CCCC.

Accrual reports will be provided to the PRMC and Cancer Center leadership. In addition, all active patients will be assessed for toxicity, SAE reports, completeness of data collection, and protocol violations. Early stopping toxicity endpoints, accrual goals and safety, and whether consent form modifications need to be made will also be reviewed.

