11.1 Anticipated Risks

The Phillips Medical's Uronav device poses no significant risk, however, any unanticipated complications or infections will be reported as stated below. The risk for prostate edema and urinary obstruction may be increased due to the additional transperineal needle placement as the biopsy will be followed by routine prostate brachytherapy. In this event, patients will be asked to maintain a Foley Catheter overnight to allowed edema to resolve, and to avoid acute obstruction the following day.

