11.3 Expectedness

Adverse Events can be Expected or Unexpected.

An expected adverse event is an event previously known or anticipated to result from participation in the research study or any underlying disease, disorder, or condition of the subject. The event is usually listed in the Investigator Brochure, consent form or research protocol. Expected acute events in this study would be an infection requiring additional antibiotic treatment beyond the standard postoperative antibiotic given for the prostate seed implant, or readmission to the hospital for pain, infection, or obstruction as a result of the biopsies.

An unexpected adverse event is an adverse event not previously known or anticipated to result from the research study or any underlying disease, disorder, or condition of the subject.

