11.8 Stopping Rules

A stopping point will be enforced if 2 or more subjects develop infections requiring IV antibiotics or infections that require hospitalization if felt to be related to the procedure (i.e for example gram negative sepsis) within 30 days of the procedure.

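### Sections 10.3 and 11.8 give different stopping rules at the same two-subject threshold: two biopsy-related admissions for obstruction or pain stop the trial under 10.3 but not under 11.8

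*Combined protocol and SAP*

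**What the plan says.** Section 10.3 (Interim Analysis) provides for continuous safety monitoring of up to 6 men and then sets the boundary: "A stopping point will be enforced if 2 or more subjects develop infections requiring IV antibiotics or require hospitalization". It gives no cause for the hospitalization, no relatedness condition and no time window.

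Section 11.8 (Stopping Rules) opens the same way and keeps the threshold of two. It limits the events to infections treated with IV antibiotics or "infections that require hospitalization if felt to be related to the procedure", within 30 days.

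Other sections bear on which events were meant:

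- Section 3.4 defines the primary safety endpoint as "the rate of infection or hospital admission within 30 days that are felt to be directly related to the procedure".
- Section 10.2 treats infection and hospitalization as separate rates: "The infection rate and hospitalization rate within 30 days due to the procedure will be collected for expected acute events".
- Section 11.1 warns: "The risk for prostate edema and urinary obstruction may be increased due to the additional transperineal needle placement".
- Section 11.3 lists among the expected events "readmission to the hospital for pain, infection, or obstruction as a result of the biopsies".
- Section 7.1 includes "assessment of urinary obstruction requiring Foley catheter placement" in the follow-up data.

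**The concern.** A stopping rule should give one answer when an event occurs. Here the answer depends on which section is open, and neither cites the other or claims precedence. A team working from 11.8, the section actually titled Stopping Rules, could treat another man after 10.3 had required a stop.

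The event in dispute is one the protocol anticipates. The study is non-therapeutic (4.1), so the added needle placements, and any obstruction they cause, come from the research. The other safeguards do not settle the matter. The pause in 11.0 is worded for unanticipated events: "If the determination is made that an unanticipated adverse event presents an unreasonable risk to subjects, the clinical evaluation will be paused". Obstruction is an anticipated risk, so that pause does not clearly cover it. The toxicity review in 11.0, the committee in 11.6 and the monitoring plan in 11.7 provide oversight, but this protocol gives them no other numeric boundary.

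**Working it through.** **Step 1: compare the text.** In 10.3 the subjects either develop an infection or require hospitalization. The two verbs share one subject, so hospitalization is a separate trigger. In 11.8 it is the infection that requires hospitalization.

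| Events in two men | Count under 10.3 | Count under 11.8 |
|---|---|---|
| Related infection with IV antibiotics, day 10 | 2: stop | 2: stop |
| Related admission for obstruction or pain, no infection, day 10 | 2: stop | 0: continue |
| Unrelated admission, or any admission after day 30 | 2: stop | 0: continue |

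The rules are nested: whatever triggers 11.8 also triggers 10.3, but not the reverse. The third row disappears if the 30-day and relatedness limits of 3.4 and 10.2 are read into 10.3. The second row remains. The calculation below uses that narrower reading of 10.3.

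**Step 2: inputs.** The number of men, 6, is from 10.3 and 4.2. The threshold, 2, is from 10.3 and 11.8. The plan states no operating characteristics for either rule, so it has no figure to reproduce. It also gives no event rates, so these are assumptions:

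- q = probability that a man has a related serious infection (counts under both rules): 5%, with 2% as an alternative.
- h = probability that a man has another related admission and no such infection: 5%, 10% or 20%.
- Men are independent.

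**Step 3: formulas.** With all related admissions counted, X ~ Bin(n, q + h). With infections only, Y ~ Bin(n, q). Each rule stops at 2 or more, and P(2 or more) = 1 − (1 − p)^n − n·p·(1 − p)^(n−1). Because the rules are nested, P(disagree) = P(X ≥ 2) − P(Y ≥ 2).

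**Step 4: worked case, n = 6, q = 0.05, h = 0.10.**

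- All related admissions: 1 − 0.85^6 − 6(0.15)(0.85^5) = 1 − 0.3771 − 0.3993 = 0.2235.
- Infections only: 1 − 0.95^6 − 6(0.05)(0.95^5) = 1 − 0.7351 − 0.2321 = 0.0328.
- Disagree: 0.2235 − 0.0328 = 0.1907.

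**Step 5: range.** Percentages are rounded from unrounded values.

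| n | q | P(stop), infections only | P(stop), all related admissions, h = 5 / 10 / 20% | P(disagree), h = 5 / 10 / 20% |
|---|---|---|---|---|
| 6 | 5% | 3.3% | 11.4 / 22.4 / 46.6% | 8.1 / 19.1 / 43.3% |
| 6 | 2% | 0.6% | 6.1 / 15.6 / 39.4% | 5.5 / 15.0 / 38.8% |
| 5 | 5% | 2.3% | 8.1 / 16.5 / 36.7% | 5.9 / 14.2 / 34.5% |

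The n = 5 row matters most for protection, because a stop reached only on the sixth man spares nobody. It is an upper bound: it assumes that all events in the first five men are known before the sixth is treated.

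**Step 6: sensitivity.** If infection and other admission are independent rather than mutually exclusive, the first row's all-admissions figures become 10.9 / 21.2 / 44.2%. If h is only 2% with q = 5% and n = 6, disagreement falls to 2.8%. A simulation of 1,000,000 trials at q = 5%, h = 10% gave disagreement of 0.190 for n = 6 and 0.142 for n = 5.

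**The case against.** The strongest reply is that the rules are nested and both are mandatory. 11.8 does not say that only its events count, so a team following the whole protocol must stop when either rule is met, and 10.3 binds. On that view the two sections are compatible and the harm arises only if 10.3 is overlooked. This is a fair account of how a careful team would act. It also means that the section titled Stopping Rules does not state the operative rule.

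A second reply is that 10.3 is shorthand for 11.8. The success criterion in 3.3.2, which allows at most one post-operative infection, gives some support to an infection-only intent. Against this, the grammar of 10.3 points the other way, 3.4 and 10.2 both count hospitalization separately from infection, and the shorthand reading still leaves 10.3 without the relatedness condition and the 30-day window.

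Third, obstruction has its own management: an overnight Foley catheter (3.3.2, 11.1) and a separate assessment of obstruction beyond 7 days (9.2). Leaving it out of the stopping rule could be deliberate. If so, the plan should say so, and 10.3 as worded contradicts it. The catheter reduces the chance of admission, and 11.3 still lists readmission for obstruction.

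Two further points stand. The rates are assumed, and the size of the disagreement depends mainly on h. And a trial stopped for two obstruction admissions might still meet the 3.3.2 success criterion. That mismatch already exists under 10.3 as written.

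**Conclusion.** The inconsistency is established from the text alone and does not depend on any event rate. Two stopping rules share one threshold, count different events, and have no stated precedence. Two biopsy-related admissions for obstruction or pain give opposite instructions.

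How often this would matter is uncertain. Under the assumed rates it ranges from a few percent of trials to over 40%, and is less when only stops early enough to spare a later man are counted. In a six-man pilot with continuous monitoring and committee oversight this does not threaten the study as a whole. It does leave the only numeric boundary unclear for a risk the protocol itself says the research may raise. It should be corrected.

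**What to change.** Put one identical rule in 10.3 and 11.8. The default should follow the admissions, relatedness and 30-day window of 3.4, and keep the IV-antibiotic threshold for infection that both sections already share. Suggested wording: *Enrolment stops once two or more subjects have had, within 30 days of the procedure and judged related to it, either an infection treated with IV antibiotics or a hospital admission for any reason, including obstruction or pain.*

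The price is a higher chance of stopping than under 11.8 alone: 22.4% against 3.3% at the assumed 5% infection and 10% other related admission. If the investigators want infections only, they should copy the 11.8 wording into 10.3 and state that admissions for obstruction or pain do not count.

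Either choice is a wording amendment to two sections. No extra data are needed, because 7.1 already collects obstruction, infection and procedure-related admission. The success criterion in 3.3.2 can stay, since it serves a different purpose from the stopping rule.

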11.0 Risk Analysis

Clinical information from subjects will be recorded onto Case Report Forms and subsequently transferred into OnCore. Patients who additionally consent to a separate Urology Registry will have their data added to the Urologic Oncology & Minimally Invasive Therapies Database for UHHS Faculty.

Should any unanticipated adverse events occur during the course of the study, the clinical research coordinator will ensure that they are documented by the investigator and reported to the appropriate IRB per its then-current guidelines. If the determination is made that an unanticipated adverse event presents an unreasonable risk to subjects, the clinical evaluation will be paused, or if deemed appropriate (to enable further investigation), the subject will be withdrawn as soon as safely possible.

Adverse events, grade 2 and above, will be captured in OnCore and will be reported in accordance with the Data and Safety Monitoring Plan (DSMP) that is approved by the Cancer Center Protocol

Review and Monitoring Committee (and aligned with the NCI-approved plan). All monitoring and reporting will be compliant with policies presented in the most current version of the CCCC Clinical Trials Operations Manual, so that an independent assessment can be made of study activities. The study will be updated to remain compliant with any changing rules/policies of the CCCC.

Accrual reports will be provided to the PRMC and Cancer Center leadership. In addition, all active patients will be assessed for toxicity, SAE reports, completeness of data collection, and protocol violations. Early stopping toxicity endpoints, accrual goals and safety, and whether consent form modifications need to be made will also be reviewed.

11.1 Anticipated Risks

The Phillips Medical's Uronav device poses no significant risk, however, any unanticipated complications or infections will be reported as stated below. The risk for prostate edema and urinary obstruction may be increased due to the additional transperineal needle placement as the biopsy will be followed by routine prostate brachytherapy. In this event, patients will be asked to maintain a Foley Catheter overnight to allowed edema to resolve, and to avoid acute obstruction the following day.

11.2 Adverse Event Definitions

An adverse event (AE) is any unfavorable or unintended event, physical or psychological, associated with a research study, which causes harm or injury to a research participant as a result of the participant's involvement in a research study. The event can include abnormal laboratory findings, symptoms, or disease associated with the research study. The event does not necessarily have to have a causal relationship with the research, any risk associated with the research, the research intervention, or the research assessments.

Adverse events may be the result of the interventions and interactions used in the research; the collection of identifiable private information in the research; an underlying disease, disorder, or condition of the subject; and/or other circumstances unrelated to the research or any underlying disease, disorder, or condition of the subject.

11.3 Expectedness

Adverse Events can be Expected or Unexpected.

An expected adverse event is an event previously known or anticipated to result from participation in the research study or any underlying disease, disorder, or condition of the subject. The event is usually listed in the Investigator Brochure, consent form or research protocol. Expected acute events in this study would be an infection requiring additional antibiotic treatment beyond the standard postoperative antibiotic given for the prostate seed implant, or readmission to the hospital for pain, infection, or obstruction as a result of the biopsies.

An unexpected adverse event is an adverse event not previously known or anticipated to result from the research study or any underlying disease, disorder, or condition of the subject.

11.4 Attribution

Attribution is the relationship between an adverse event or serious adverse event and the study drug. Attribution will be assigned as follows:

- Definite – The AE is clearly related to the study device or procedures.
- Probable – The AE is likely related to the study device or procedures.
- Possible – The AE may be related to the study device or procedures.
- Unlikely – The AE is doubtfully related to the study device or procedures.
- Unrelated – The AE is clearly NOT related to the study device or procedures.

11.5 Reporting Procedures for All Adverse Events

All participating investigators will assess the occurrence of AEs throughout the subject's participation in the study. Subjects will be followed for adverse events for 3 months after the Uronav guided biopsy or until death, whichever occurs first. The clinical course of each event will be followed until resolution, stabilization, or until it has been determined that the study treatment or participation is not the cause.

The investigator is responsible for ensuring that all adverse events observed by the investigator or reported by the subject which occur after the subject has signed the informed consent are fully recorded in the subject's case report form, subject's medical records, and/or any other institutional requirement. Source documentation must be available to support all adverse events.

A laboratory test abnormality considered clinically relevant (e.g., causing the subject to withdraw from the study), requiring treatment or causing apparent clinical manifestations, or judged relevant by the investigator, should be reported as an adverse event.

The investigator will provide the following for all adverse events:

- Description of the event
- Date of onset and resolution
- Grade of toxicity
- Attribution of relatedness to the investigational device or procedures
- Action taken as a result of the event
- Outcome of event

In this study, descriptions and grading scales found in the NCI Common Terminology Criteria for Adverse Events (CTCAE) version 4.0 available at <http://ctep.cancer.gov> will be utilized for AE reporting.

Serious Adverse Events

A **serious adverse event** (SAE) is any adverse experience occurring that is attributed to the research device that results in any of the following outcomes:

- Results in **death**.
- Is a **life-threatening** adverse experience. The term life-threatening in the definition of serious refers to an adverse event in which the subject was at risk of death at the time of

the event. It does not refer to an adverse event which hypothetically might have caused death if it were more severe.

- Requires **inpatient hospitalization or prolongation of existing hospitalization**. Any adverse event leading to hospitalization or prolongation of hospitalization will be considered as Serious, UNLESS at least one of the following expectations is met:
 - The admission results in a hospital stay of less than 24 hours OR
 - The admission is pre-planned (e.g., elective or scheduled surgery arranged prior to the start of the study) OR
 - The admission is not associated with an adverse event (e.g., social hospitalization for purposes of respite care).

However it should be noted that invasive treatment during any hospitalization may fulfill the criteria of “medically important” and as such may be reportable as a serious adverse event dependant on clinical judgment. In addition where local regulatory authorities specifically require a more stringent definition, the local regulation takes precedent.

- Results in **persistent or significant disability/incapacity**. The definition of disability is a substantial disruption of a person’s ability to conduct normal life’s functions.
- Is a **congenital anomaly/birth defect**.
- Is an **important medical event**. Important medical events that may not result death, be life-threatening, or require hospitalization may be considered a serious adverse experience when, based upon appropriate medical judgment, they may jeopardize the subject and may require medical or surgical intervention to prevent one of the outcomes listed in this definition. Examples of such medical events include allergic bronchospasm requiring intensive treatment in an emergency room or at home, blood disease or disorders, or convulsions that do not result in inpatient hospitalization, or the development of drug dependency or drug abuse. The development of a new cancer is always considered an important medical event.

SAE Report Form

SAEs will be recorded on the FDA Form 3500A (MedWatch) but should only be reported as instructed below. The electronic FDA SAE reporting forms should not be used.

Reporting Procedures for Serious Adverse Events

For the purposes of safety reporting, all adverse events will be reported that occur on or after Biopsy through Visit 5. Adverse events, both serious and non-serious, and deaths that occur during this period will be recorded in the source documents. All SAEs should be monitored until they are resolved or are clearly determined to be due to a subject’s stable or chronic condition or intercurrent illness(es). Related AEs will be followed until resolution to baseline or grade 1 or stabilization.

SAE Reporting Requirements

- The Site Principal Investigator will review the SAE and report the event to the FDA, external collaborator(s), and IRB as applicable.
- It is the Sponsor-Investigator’s responsibility (e.g. lead site PI) to ensure that ALL serious adverse events that occur on the study (e.g. ALL SAEs that occur at each enrolling institution) are reported to all participating sites.

Institutional Review Board Reporting Requirements:

- Investigative sites will report adverse events to their respective IRB according to the local IRB's policies and procedures in reporting adverse events.

SAEs and OnCore

- All SAEs will be entered into OnCore.
- A copy of the SAE form(s) submitted to the sponsor-investigator is also uploaded into OnCore.

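### The SAE definition in 11.5 requires attribution to the device, so a serious harm attributed only to the biopsy procedure can miss SAE reporting

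*Combined protocol and SAP*

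**What the plan says.** The Serious Adverse Events part of 11.5 defines an SAE as "any adverse experience occurring that is attributed to the research device" that results in one of the outcomes then listed: death, a life-threatening event, hospitalization, disability, congenital anomaly or an important medical event. The attribution condition comes before the list, so it applies to all of them. Procedures are not mentioned.

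Under the hospitalization outcome, three kinds of admission are not counted as serious. The first reads "The admission results in a hospital stay of less than 24 hours OR". The other two are pre-planned admissions and admissions not associated with an adverse event.

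Other sections describe relatedness differently:

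- 11.4 grades every adverse event and SAE on a five-level scale. Its top level is "The AE is clearly related to the study device or procedures", and it runs down to clearly not related.
- The list in 11.5 of data to record for each adverse event includes "Attribution of relatedness to the investigational device or procedures".
- 11.3 gives the expected acute events as infection needing extra antibiotics, or "readmission to the hospital for pain, infection, or obstruction as a result of the biopsies".
- 3.4 makes the primary safety endpoint "the rate of infection or hospital admission within 30 days that are felt to be directly related to the procedure".
- 11.8 counts infections needing IV antibiotics, or "infections that require hospitalization if felt to be related to the procedure", within 30 days of the procedure.

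Under 11.5, SAEs go on a MedWatch form, and the site investigator reports them to the FDA, collaborators and IRB as applicable. Under 11.6, SAEs go to the Data and Safety Toxicity Committee at the same time as they go to the sponsor or regulators.

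**The concern.** Uronav guides the needle. Section 6.1 has the samples taken by hand with a biopsy gun or through a trocar. Section 11.1 says the device carries no significant risk and puts the added risk of edema and obstruction down to needle placement. The harms that the protocol itself expects are therefore ones that an investigator may properly attribute to the biopsy procedure and not to the device. A definition that admits only device-attributed events then leaves them outside the SAE category, however severe they are.

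At stake is prompt, event-by-event reporting to the bodies that oversee the trial. Besides SAE submission, 11.6 names only an annual report to the toxicity committee. In a six-patient pilot planned to last one year (3.1), an annual report may arrive after most or all patients have been treated. The attribution judgment also rests with investigators, one or more of whom consult for the device maker (16.0). That is a further reason not to let seriousness depend on device causality.

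**Working it through.** The plan gives no figure on this point, so the check compares the passages and follows sample events through them.

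**Step 1: is the device condition consistent with the rest of section 11?** It is not, for three reasons.

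- 11.4 applies its scale to SAEs and includes unlikely and unrelated levels. Under the 11.5 definition, an SAE clearly unrelated to both device and procedures could not exist.
- 11.5 itself has SAEs followed until they resolve or are found to be due to a stable or chronic condition or intercurrent illness. That presumes some SAEs are not caused by the device.
- The attribution item in 11.5 covers device or procedures, yet the SAE definition later in the same section covers the device alone.

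Section 11.2 adds a little: it says of an adverse event that "The event does not necessarily have to have a causal relationship with the research". But the same paragraph opens by describing harm that results from taking part in the research, so it is mixed evidence and the point does not rest on it.

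**Step 2: which events does each rule catch?**

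| Event within 30 days | Counts for 3.4 | Counts for 11.8 | SAE under 11.5 |
|---|---|---|---|
| Sepsis, stay of 24 hours or more, attributed to the biopsy but not to Uronav | Yes | Yes | No: fails the device condition |
| Infection admission under 24 hours, attributed to the biopsy but not to Uronav | Yes | Yes | No: fails the device condition, and the stay is also exempt |
| Admission under 24 hours for obstruction, same attribution | Yes | No: not an infection | No, for the same two reasons |
| Sepsis, stay under 24 hours, attributed to Uronav | Yes, if also felt related to the procedure | Yes, if also felt related to the procedure | Not through hospitalization, but possibly as life-threatening or, by judgment, as an important medical event |

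The first row shows the main defect, and sepsis is the example that 11.8 itself gives. The last row shows that the 24-hour exemption is secondary: it touches only the hospitalization outcome, and the other outcomes stay open once the device condition is met.

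**Step 3: what depends on the SAE label?**

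- Depends on it: the MedWatch form, SAE reporting to the FDA and collaborators (11.5), and submission to the toxicity committee (11.6).
- Does not depend on it: the endpoint in 3.4, the stopping rules in 10.3 and 11.8, and the follow-up in 7.1, which collects procedure-related infection and admission directly. Recording of all adverse events from biopsy to Visit 5 (11.5), OnCore capture of grade 2 and above (11.0) and adverse event reporting to the IRB (11.5) are also independent of it.

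**Step 4: does the safety rate or the trigger move?** One event in 6 men is 1/6 = 16.7%, and the trigger is 2 subjects. Both are counted from the events themselves. An event without the SAE label is still counted, so the change in the rate is 0 percentage points and the trigger still fires at 2.

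**The case against.** The strongest reply is that little is lost. All adverse events from biopsy to Visit 5 are reported and recorded, and those of grade 2 and above enter OnCore and are reported under the Data and Safety Monitoring Plan. Section 11.1 says infections will be reported, and 11.0 lists early stopping toxicity endpoints among the matters reviewed. This stands as a limit on the consequence. It does not repair the definition, because the submission to the toxicity committee that 11.6 requires is tied to SAEs. The monitoring plan is not reproduced, so whether it closes the gap cannot be seen.

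A second reply is that an investigator might attribute an infection after a Uronav-guided biopsy to the device. Sections 3.3.2 and 10.2 do tie infection to the evaluation of Uronav. This also stands: exclusion is possible, not certain. But whether a serious infection is reported as an SAE should not turn on that choice.

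A third is that an endpoint may count admissions that an SAE definition does not, and that 11.5 lets a more stringent local definition take precedence. That is fair, and it is why the 24-hour exemption is treated here as a gap to cover and not as a contradiction.

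A reader might go further and infer that the committee would see 1 event in 6 where there were 2, that the safety rate would fall by 17 points, or that the IRB would not be told. The documents support none of these. No section says the stopping rule is applied by counting SAE submissions, the rate is not built from SAE forms, and 11.5 has sites report adverse events to the IRB without limiting this to SAEs.

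**Conclusion.** The SAE definition is wrong as written: it conflicts with 11.3, 11.4 and the attribution item in 11.5, and does not match the procedure-related events in 3.4 and 11.8. Followed literally, it leaves out serious forms of the harms the trial expects whenever they are attributed to the biopsy and not to Uronav. The loss is confined to three SAE-specific routes: the MedWatch form, SAE reporting to the FDA and collaborators, and submission to the toxicity committee. The safety rate and the two-subject trigger are not altered.

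This rests on a literal reading of 11.5 and on an investigator who separates procedure from device when attributing an event. It also assumes that the monitoring plan, which is not in the documents, does not already require such events to be submitted. The case for changing the text is that the correction is specific and almost free, not that any reported figure would be in error.

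**What to change.** In 11.5, define an SAE as any adverse event that meets a listed outcome, regardless of attribution. Record relatedness to device or procedures separately under 11.4, and correct the reference there to a study drug.

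Add one sentence to 11.5 or 11.6: any event that counts toward 3.4 or 11.8 is also sent to the toxicity committee, whatever the length of stay.

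Sections 10.3 and 11.8 must also be reconciled. The first counts hospitalization with no condition on relatedness and no time window. The second is limited to infections, applies a relatedness condition and sets a 30-day window. For that reason the added sentence refers to 3.4 and 11.8 and leaves 10.3 out until the two agree.

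The cost is a short wording amendment and at most a few extra SAE forms in 6 men. No clinical procedure changes.
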